Liver-associated enzymes and TB will be summarized by the value and change from baseline in the value, by treatment group and visit. In addition, the number and percent of patients with abnormal values for ALT, AST, and TB will be summarized. These summaries of patients with abnormal values will be performed overall; by normal baseline; and by abnormal baseline for each of ALT, AST, and TB. Hy's law criteria ($\geq 3 \times$ ULN for either ALT or AST, with accompanying TB $> 2 \times$ ULN or patient's baseline) will also be applied to the data; any potential Hy's law cases will be listed separately. In the case of patients with Gilbert's disease, TB will be fractionated and the determination of $2 \times$ ULN based upon direct (conjugated) bilirubin.

Musculoskeletal Safety

AEs of muscle-related symptoms will be summarized by treatment group. CK levels will be summarized by the value and change from baseline in the value, by treatment group and visit. In addition, the number and percent of patients with abnormal CK values will be summarized. These summaries of patients with abnormal CK will be performed overall; by normal baseline CK; and by abnormal baseline CK.

Diabetes and Hyperglycemia

Cases of new onset of diabetes will be recorded as AEs and will be summarized using the appropriate SOC. These events will be summarized by severity and relationship to study drug for each treatment group. Glucose and HbA_{1C} will be monitored at baseline and at Weeks 12 and 24 and be summarized.

Renal Safety

Baseline eGFR will be summarized by treatment group for actual value and for baseline eGFR categories. Shift tables of eGFR category from baseline over the study, will be provided by treatment group. Shift tables of urine protein (negative/positive) from baseline over the study, will be provided by treatment group. Values of CK over the study will be summarized by treatment group and by baseline eGFR category. Finally, muscle-related AEs will be summarized by treatment group and by baseline eGFR category.

Neurocognitive Events

Neurocognitive events will be identified and evaluated by routine safety monitoring of PE findings and AEs. Summarization of neurocognitive events will occur using prespecified Medical Dictionary for Regulatory Activities (MedDRA) terms and will be performed by SOC, severity, and relationship to study drug for each treatment group.

Clinical Endpoints

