2. SYNOPSIS

Name of Sponsor: Esperion Therapeutics, Inc.
Name of Investigational Product: Bempedoic Acid (ETC-1002) [REDACTED] tablets
Name of Active Ingredient: Bempedoic acid (ETC-1002)
Title of Study: A Long-term, Randomized, Double-blind, Placebo-controlled, Multicenter Study to Evaluate the Efficacy of Bempedoic Acid (ETC-1002) in Patients with Hyperlipidemia at High Cardiovascular Risk Not Adequately Controlled by Their Lipid-Modifying Therapy
Study Number: 1002-047
Phase of Development: 3
Clinical Sites: Approximately 125 sites located in North America and Europe
Objectives: Primary: 
To assess the 12-week efficacy of bempedoic acid (ETC-1002) 180 mg/day versus placebo in decreasing low-density lipoprotein cholesterol (LDL-C) in high cardiovascular (CV) risk patients with hyperlipidemia (with underlying heterozygous familial hypercholesterolemia [HeFH] and/or atherosclerotic cardiovascular diseases [ASCVD]) who are not adequately controlled with their maximally tolerated lipid-modifying therapy. Secondary: 
To evaluate the effect of 24-week treatment with bempedoic acid 180 mg/day versus placebo on LDL-C.To evaluate the effect of bempedoic acid 180 mg/day versus placebo on non-high-density lipoprotein cholesterol (non-HDL-C), total cholesterol (TC), high-sensitivity C-reactive protein (hs-CRP), and apolipoprotein B (apoB) after 12 weeks of treatment. Tertiary: 
To evaluate the effect of long-term (52-week) treatment with bempedoic acid 180 mg/day versus placebo on LDL-C, non-HDL-C, TC, high-density lipoprotein cholesterol (HDL-C), triglycerides (TG), hs-CRP, and apoB.To evaluate the long-term (52-week) safety and tolerability of bempedoic acid 180 mg/day compared to placebo.

Methodology:

1002-047 STUDY DESIGN

Study Design:

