In addition, a summary of percent change from baseline to Week 12 LDL-C using the FAS, excluding patients who received additional lipid-lowering therapy by that time point (by Week 12 for the Week 12 time point), will be provided. Percent change from baseline to Weeks 24 and 52 on LDL-C will be analyzed similarly, with patients in the FAS who did not receive additional LDL or triglyceride-lowering therapy by that time point (by Week 24 for the Week 24 analysis by Week 52 for the Week 52 analysis) included in the analyses. Output from each time point will include the LSM and SE for each treatment group, as well as the placebo-corrected LSM, 95% CI, and p-value.

Additional post-randomization adjunctive lipid-modifying therapy

The number and percent of patients in each treatment group requiring additional (post-randomization) adjunctive lipid-modifying therapy will be summarized. Medications and the reasons for their additional treatment (hyperlipidemia vs. hypertriglyceridemia) will be summarized separately.

Safety Analyses

The summarization of AEs will include TEAEs, defined as AEs with an onset date on or after initiation of study treatment. TEAEs and SAEs will be summarized by system organ class (SOC), severity, and relationship to study drug for each treatment group. These AE summaries will include cumulative incidence (percent of patients experiencing the AE) and patient-year adjusted incidence rates. If appropriate, absolute and relative risk differences will be calculated using both cumulative incidence and incidence rates. Deaths, withdrawal from study treatment due to AEs, and withdrawal from the study due to AEs will each be summarized by treatment group.

Clinical safety laboratories, including hematology, blood chemistry, coagulation, HbA_{1c}, glucose, and urinalysis; PE findings; vital signs; ECG readings; and weight will be summarized by the value and by change from baseline in the value (where appropriate) at each postbaseline time point.

Hepatic Safety

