12.8. Safety Endpoints

The summarization of AEs will include TEAEs. TEAEs and SAEs will be summarized by SOC, severity, and relationship to study drug for each treatment group. These AE summaries will include cumulative incidence (percent of patients experiencing the AE) and patient-year adjusted incidence rates. If appropriate, absolute and relative risk differences will be calculated using both cumulative incidence and incidence rates. Deaths, withdrawal from study treatment due to AEs, and withdrawal from the study due to AEs will each be summarized by treatment group.

Clinical safety laboratories, including hematology, blood chemistry, coagulation, HbA_{1C}, glucose, and urinalysis; PE findings; vital signs; ECG readings; and weight will be summarized by the value and by change from baseline in the value (where appropriate) at each postbaseline time point.

Hepatic Safety

Liver-associated enzymes and TB will be summarized by the value and change from baseline in the value, by treatment group and visit. In addition, the number and percent of patients with abnormal values for ALT, AST, and TB will be summarized. These summaries of patients with abnormal values will be performed overall; by normal baseline; and by abnormal baseline for each of ALT, AST, and TB. Hy's law criteria ($\geq 3 \times$ ULN for either ALT or AST, with accompanying TB $> 2 \times$ ULN or patient's baseline) will also be applied to the data; any potential Hy's law cases will be listed separately. In the case of patients with Gilbert's disease, TB will be fractionated and the determination of $2 \times$ ULN based upon direct (conjugated) bilirubin. For patients with Gilbert's Disease $2 \times$ the conjugated bilirubin will be used as the criterion.

Musculoskeletal Safety

AEs of muscle-related symptoms will be summarized by treatment group. CK levels will be summarized by the value and change from baseline in the value, by treatment group and visit. In addition, the number and percent of patients with abnormal CK values will be summarized. These summaries of patients with abnormal CK will be performed overall; by normal baseline CK; and by abnormal baseline CK.

Diabetes and Hyperglycemia

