- Added a line for Amendment 3 version and date to reflect amendment version details.
- Prohibited use of simvastatin ≥ 40 mg/day [REDACTED]

[REDACTED] The protocol has been amended to exclude patients receiving simvastatin ≥ 40 mg and remove study visits at Weeks 16, 20, 28, and 32 that were only for patients taking simvastatin 40 mg/day. A letter was provided to all investigators with instructions on how to proceed for enrolled patients receiving simvastatin 40 mg/day.

- Increased number of patients to be enrolled from approximately 525 to approximately 750 with 500 randomized to bempedoic acid and 250 randomized to matching placebo as was included in the original protocol and Amendment 1. The reason for the increase in patients is due to the recent decision to discontinue IMP in patients receiving simvastatin 40 mg/day across our program. Based on this decision, the safety database will be smaller than anticipated; therefore, we would like to increase the number of patients in this protocol to 750 as originally planned to ensure a robust safety database.
- Clarified that the requirement to have $\geq 80\%$ treatment compliance during the Run-in Period refers to the average treatment compliance over the entire Run-in Period (compliance measured at Visits S3 and T1).
- Corrected the visit window for Week 24 within the protocol text and Appendix 1, Schedule of Events, to reflect 168 ± 7 days.
- Updated the definition of SAEs to include hospitalizations for preplanned surgeries and/or elective surgeries.

CHANGE 1 REVISION OF TITLE PAGE VERSION INFORMATION

Location:

Title Page

Original Text:

Version	Date
Amendment 1:	18 January 2017
Amendment 2:	22 March 2017

New Text:

Version	Date
Amendment 1:	18 January 2017
Amendment 2:	22 March 2017
Amendment 3:	09 May 2017

CHANGE 2 REVISION TO LOCATION OF SITES

Location:

Section 2, Synopsis

Original Text:

Clinical Sites: Approximately 125 sites located TBD

New Text:

[figure not shown]
Clinical Sites: Approximately 125 sites located ~~TBD~~ *in North America and Europe*

CHANGE 3 STUDY DESIGN FIGURE REVISIONS

[figure not shown]
Location:

Section 2, Synopsis; 6.1 Overall Study Design

Original Text:

New Text:

CHANGE 4 SUBJECT EXCLUSION CRITERIA REVISIONS

Location:

Section 2, Synopsis; Section 7.2, Subject Exclusion Criteria

Original Text:

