18. SAFETY OUTCOMES

All outputs for safety outcomes will be based on the Safety Analysis Set.

There will be no statistical comparisons between the treatment groups for safety data, unless otherwise specified with the relevant section.

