18.1.1. ALL TEAEs

Incidence of TEAEs will be presented by System Organ Class (SOC) and Preferred Term (PT) and also broken down further by maximum severity and relationship to study medication. TEAEs will also be presented by PT in descending frequency. Adverse events by the subgroups in [Section 17.2.4](#) with the exception of baseline LDL subgroup will also be presented.

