18.1.4. TEAEs LEADING TO DISCONTINUATION OF STUDY MEDICATION

TEAEs leading to permanent discontinuation of study medication will be identified by using the

Statistical Analysis Plan

response of 'Drug Withdrawn/Permanently discontinued' on the Action Taken With Study Drug Field on the AE eCRF page. For TEAEs leading to discontinuation of study medication, summaries of incidence rates (frequencies and percentages) by SOC and PT will be prepared.

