18.3. CLINICAL ENDPOINTS

Clinical endpoints will be monitored and adjudicated by an independent blinded expert CEC for this study. The following clinical endpoints will be tabulated:

- CV death (MACE)
- Non-CV death (non-MACE)
- Nonfatal myocardial infarction [MI] (MACE)
- Nonfatal stroke (MACE)
- Hospitalization for unstable angina (MACE)
- Coronary revascularization (MACE)
- Non-coronary arterial revascularization (non-MACE)
- Hospitalization for heart failure (non-MACE)

Statistical Analysis Plan

Additional details regarding clinical endpoints and clinical endpoint definitions will be included in CEC charter. The number of patients with at least one adjudicated event and incidences and percentage of patients with each event will be presented in a table.

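### The protocol provides, if appropriate, for between-arm risk differences for adverse events, but SAP 18 plans no between-arm estimate for safety data

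*Protocol*

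**What the plan says.** **Protocol.** The Synopsis (Safety Analyses) and Section 12.8 carry the same two statements about AE summaries. The first covers the scales: "These AE summaries will include cumulative incidence (percent of patients experiencing the AE) and patient-year adjusted incidence rates". The second covers the comparison: "If appropriate, absolute and relative risk differences will be calculated using both cumulative incidence and incidence rates". The tertiary safety objective is comparative: "To evaluate the long-term (52-week) safety and tolerability of bempedoic acid 180 mg/day compared to placebo". SAP 2.3 keeps that comparison with placebo.

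**SAP.** Section 18 opens its safety plan with a general rule: "There will be no statistical comparisons between the treatment groups for safety data, unless otherwise specified with the relevant section". The sections that follow describe by-arm output. All TEAEs (18.1.1) get incidence by system organ class and preferred term. For TEAEs leading to discontinuation (18.1.4), "summaries of incidence rates (frequencies and percentages) by SOC and PT will be prepared". For adjudicated clinical endpoints (18.3), "The number of patients with at least one adjudicated event and incidences and percentage of patients with each event will be presented in a table".

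**Which governs.** Protocol 12.1 gives the SAP precedence over the protocol on analysis. SAP 4.2 defines the final analysis as what the SAP identifies.

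**The concern.** The protocol foresees a between-arm estimate for adverse events on two scales. The governing document does not carry it forward and gives no reason. The analysis team would therefore produce side-by-side percentages and stop there.

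At stake is what the trial can say about safety. Percentages by arm let a reader subtract one from the other. They do not show how large an excess the data have excluded, or whether an apparent absence of difference is informative. The patient-year rates named in the protocol are also missing from the SAP text. In 18.1.4 the term incidence rate is defined as frequencies and percentages, so person-time drops out as well. If the arms differ in time on treatment, the two scales can tell different stories.

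**Working it through.** **1. The plan's own figure.** SAP 7.1 states more than 95% power with 500 against 250 patients, a 15-point difference, SD 15 and two-sided 5%. The standardized difference is 15 / (15 × sqrt(1/500 + 1/250)) = 1 / 0.0775 = 12.9, so power exceeds 99.9% and the statement is correct. About 20 placebo patients (with 40 on active) would already give 95% power. The size is thus not driven by the primary endpoint. Protocol 6.2 says the 750 patients also serve long-term safety data, and the Amendment 3 rationale in Appendix 8 says the return to 750 was "to ensure a robust safety database".

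**2. Does any SAP section use the exception in SAP 18?**

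| SAP section | Planned output | Between-arm estimate |
|---|---|---|
| 18.1.1 to 18.1.3 TEAEs | incidence, severity, relationship | none |
| 18.1.4 Discontinuation | frequencies and percentages | none |
| 18.1.5, 18.1.6 SAEs, AESIs | summaries | none |
| 18.2 Deaths | listing | none |
| 18.3 Clinical endpoints | counts and percentages | none |
| 18.4 Laboratory | descriptives, shifts, abnormality tables | none |
| 18.5 to 18.7 ECG, vital signs, examination | shift, change from baseline, listing | none |

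No table title in SAP Appendix 3 (DMC outputs) or in the post-hoc addendum names a risk difference, ratio, interval or patient-year rate.

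**3. Count of planned between-arm AE estimates.** Protocol: two types (absolute, relative) on two scales (cumulative incidence, incidence rate), if appropriate. SAP: none. Planned confidence intervals for safety differences: none in either document.

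**4. What an interval would add.** The documents give no AE rates for planning, so the counts below are assumptions. The Newcombe interval combines the Wilson limits (l, u) of each arm:

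lower = d − sqrt[(p1 − l1)² + (u2 − p2)²]; upper = d + sqrt[(u1 − p1)² + (p2 − l2)²]

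For 20/500 against 5/250, the Wilson limits are 2.60% to 6.10% and 0.86% to 4.60%, and d = 4.0 − 2.0 = 2.0 points.

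- Lower: 2.0 − sqrt(1.40² + 2.60²) = 2.0 − 2.95 = −1.0
- Upper: 2.0 + sqrt(2.10² + 1.14²) = 2.0 + 2.39 = +4.4

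| Assumed events (500 v 250) | Difference, points | 95% interval |
|---|---|---|
| 10 v 2 | +1.2 | −1.1 to +2.9 |
| 20 v 5 | +2.0 | −1.0 to +4.4 |
| 50 v 12 | +5.2 | +1.1 to +8.8 |
| 100 v 50 | 0.0 | −6.3 to +5.8 |

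As a general guide, the half-width at a common rate p is 1.96 × sqrt[p(1 − p)(1/500 + 1/250)]. This gives about ±1.5 points at 1%, ±2.1 at 2%, ±3.3 at 5%, ±4.5 at 10% and ±6.1 at 20%. The patient-year scale cannot be illustrated in the same way, because the documents give no discontinuation figure.

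**The case against.** Several points on the other side stand.

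- **The protocol is conditional.** It says the differences will be calculated if appropriate, so leaving them out breaks no firm commitment. Even so, the SAP is the place to decide what is appropriate, and it gives a general rule without a reason.
- **No interval was ever promised.** A reader might infer that the SAP removed confidence intervals that the protocol had planned. The documents do not support this: neither plans one.
- **The scope is AE summaries only.** A reader might infer that laboratory abnormalities and adjudicated endpoints lost a planned comparison too. They did not. Protocol 12.8 gives them number and percent, or a summary by event type and arm, much as SAP 18.3 and 18.4 do.
- **The SAP rule may mean tests only.** A statistical comparison can be read as a hypothesis test, so a descriptive risk difference is not clearly forbidden. That does not help the analyst, because no section specifies one.
- **The templates are not available.** SAP 8 and 18.1 refer to table templates for content. A difference column there is possible, though SAP 18 asks for the specification in the relevant section.
- **Crude differences can be derived.** Percentages by arm are planned, so 2:1 allocation does not prevent comparison, and a reader could compute a crude interval from the counts. This does not extend to patient-year rates, which need person-time.
- **Program-level pooling.** Protocol 11.6 aggregates clinical endpoints across the Phase 3 studies, and the Amendment 3 rationale concerns the safety database. Interval precision within this trial was not the stated purpose of the extra patients.

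**Conclusion.** The point holds in a narrow form. The protocol provides conditionally for absolute and relative differences in AE incidence on two scales. The governing SAP provides for none, and the objective in both documents remains a comparison with placebo. The patient-year rates are likewise not carried forward. The missing interval is a shared gap, not a contradiction.

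A reader might go further and conclude that the safety objective is unanswered or that the plan forbids any comparison. Neither follows: concurrent by-arm percentages do address a tertiary descriptive objective, and the rule in SAP 18 contains an exception that simply goes unused.

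No stated figure changes. The size is the precision left unreported, roughly ±1.5 to ±6 points for common event rates of 1% to 20%. It rests on assumed rates, full 500/250 denominators, and the templates containing no such column. This is a cheap improvement worth making, not an error that threatens the trial's conclusions.

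**What to change.** In SAP 18, replace the general rule with text to this effect: no hypothesis tests will be done on safety data. For any TEAE, serious TEAEs, TEAEs leading to discontinuation and each AESI category, the risk difference and relative risk (bempedoic acid versus placebo) will be given with 95% confidence intervals. Patient-year adjusted incidence rates by arm, and the rate difference and rate ratio with 95% confidence intervals, will be given for the same outcomes, as Protocol 12.8 provides. All are descriptive, with no p-values and no multiplicity adjustment. Name the interval method, for example Newcombe or Miettinen-Nurminen for the risk difference, and define the person-time denominator.

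The same columns for adjudicated clinical endpoints are optional, since neither document planned them.

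The cost is SAP wording and a few columns in existing tables, with no new data and no change to conduct. The downside is that some unadjusted intervals will exclude no difference by chance; the descriptive label should be printed on the tables for that reason.

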3. LIST OF ABBREVIATIONS AND DEFINITIONS OF TERMS

The following abbreviations and specialist terms are used in this study protocol.

Table 1: Abbreviations and Specialist Terms

Abbreviation or Specialist Term	Explanation
ACL	Adenosine triphosphate-citrate lyase
ACS	Acyl-CoA synthetase
ADR	Adverse drug reaction
AE	Adverse event
AESI	Adverse events of special interest
ALB	Albumin
ALK-P	Alkaline phosphatase
ALT	Alanine aminotransferase
ANCOVA	Analysis of covariance
apoB	Apolipoprotein B
ASCVD	Atherosclerotic cardiovascular diseases
AST	Aspartate aminotransferase
ATP	Adenosine triphosphate
AUC	Area under the concentration-time curve
AUC ₀₋₂₄	Area under the curve during 24 hours
BMI	Body mass index
BP	Blood pressure
BUN	Blood urea nitrogen
Ca	Calcium
CABG	Coronary artery bypass graft
CEC	Clinical Event Committee
CETP	Cholesterol ester transfer protein
CFR	Code of Federal Regulations
CHD	Coronary heart disease
CI	Confidence interval
CK	Creatine kinase
Cl	Chloride
C _{max}	Time to peak maximum concentrations
CMV	Cytomegalovirus
CNS	Central nervous system
CoA	Acetyl-coenzyme A

Abbreviation or Specialist Term	Explanation
CO ₂	Carbon dioxide
CRO	Contract research organization
CT	Computed tomography
CTA	Computed tomographic angiography
CV	Cardiovascular
CYP	Cytochrome P450
DBP	Diastolic blood pressure
DMC	Data Monitoring Committee
ECG	Electrocardiogram
eCRF	Electronic case report form
EDC	Electronic data capture
eGFR	Estimated glomerular filtration rate
EMA	European Medicines Agency
EOS	End of Study
ETC-1002	Bempedoic acid
EU	European Union
FAS	Full analysis set
FDA	Food and Drug Administration
FPFV	First patient first visit
FSH	Follicle-stimulating hormone
GCP	Good Clinical Practice
GI	Gastrointestinal
HbA _{1c}	Glycosylated hemoglobin, Type A1C
HBsAg	Hepatitis B surface antigen
Hct	Hematocrit
HCV	Hepatitis C virus
HCV-AB	Hepatitis C antibodies
HDL-C	High-density lipoprotein cholesterol
HeFH	Heterozygous familial hypercholesterolemia
Hgb	Hemoglobin
HMG-CoA	3-hydroxy-3-methylglutaryl-coenzyme A
hs-CRP	High-sensitivity C-reactive protein
IB	Investigator's Brochure
ICD	Informed Consent Document
ICH	International Conference on Harmonisation
IEC	Independent Ethics Committee

Abbreviation or Specialist Term	Explanation
IMP	Investigational medicinal product
IND	Investigational New Drug Application
INR	International normalized ratio
IRB	Institutional Review Board
ITT	Intention-to-treat
IUD	Intrauterine device
IWRS	Interactive web response system
K	Potassium
LDH	Lactate dehydrogenase
LDL-C	Low-density lipoprotein cholesterol
LDLR	LDL receptor
LFT	Liver function test
LPLV	Last patient last visit
LS	Least square
LSM	Least square mean
MACE	Major adverse cardiac event
MCH	Mean corpuscular hemoglobin
MCHC	Mean corpuscular hemoglobin concentration
MCV	Mean corpuscular volume
MDRD	Modification of diet in renal disease
MED ID	Medication identification
MedDRA	Medical Dictionary for Regulatory Activities
MI	Myocardial infarction
MRI	Magnetic resonance imaging
Na	Sodium
NA	Not applicable
NIMP	Non-investigational medicinal product(s)
NLA	National Lipid Association
NOAEL	No-observed-adverse-effect level
non-HDL-C	Non-high-density lipoprotein cholesterol
PAD	Peripheral arterial disease
PCI	Percutaneous coronary intervention
PCSK9	Proprotein convertase subtilisin/kexin type 9
PE	Physical exam
PK	Pharmacokinetic(s)
PMM	Pattern mixed model

Abbreviation or Specialist Term	Explanation
PT	Prothrombin time
RBC	Red blood cell
RNA	Ribonucleic acid
SAE	Serious adverse event
SAP	Statistical Analysis Plan
SBP	Systolic blood pressure
SE	Standard error
SGOT	Serum glutamic oxaloacetic transaminase
SGPT	Serum glutamic pyruvic transaminase
SOC	System organ class
SOP	Standard operating procedures
SP	Safety population
SUSARS	Suspected and unexpected serious adverse reactions
$t_{1/2}$	Terminal elimination half-live
T2DM	Type 2 diabetes mellitus
TB	Total bilirubin
TC	Total cholesterol
TEAE	Treatment-emergent adverse event
TG	Triglycerides
TIA	Transient ischemic attack
TSH	Thyroid-stimulating hormone
TQT	Thorough QT/QTc
ULN	Upper limit of normal
US	United States
WBC	White blood cell
WHO	World Health Organization

